## ***Study Protocol***

**Objectives.** While an intellectually active and socially integrated lifestyle shows promise for promoting cognitive resilience with aging, the mechanisms underlying any such effects are not well understood (Stine-Morrow et al., 2014, 2021; Stine-Morrow & Manavbasi, 2022). The aim of the current project was to test the implications of the “Mutualism” hypothesis (Savi et al., 2019; van der Maas et al., 2006; van der Maas et al., 2017), which suggests that intellectual function emerges out of the reciprocal influence of growth in abilities as they are exercised in the ecology of everyday life. Such a view stands in contrast to the Principle of Direct Transfer (Thorndike, 1906) in suggesting that improvement in one component will enhance the *modifiability* of a related component. In other words, while conventional conceptualizations of transfer imply immediate generalization, mutualism assumes that practice in the novel skill is required for benefits to be manifest. An additional aim was to test the idea that mutualistic effects will be enhanced by more diverse training in related skills, relative to single-component training (Brown et al., 2014; Schmidt & Bjork, 1992).

To this end, participants engaged in two phases of training. The target task in Phase 2 was the complex reading span, which has been found to be predictive of standardized tests of verbal ability and measures of language comprehension (Baddeley, 2012; Daneman & Carpenter, 1980; Daneman & Merikle, 1996; Payne & Stine-Morrow, 2017; Peng et al., 2022; Stine & Wingfield, 1987). As a WM task, the reading span requires the concurrent management of sentence processing and a memory load. Participants were randomly assigned to one of four groups that varied in the type of training in Phase 1. In the Different Mixed (DM) condition, participants practiced lexical decision span and category span tasks, two different tasks similar to the reading span in requiring the individual to manage a memory load while processing verbal material but with different sorts of processing components. In the Different Single (DS) condition, participants practiced only the lexical decision span, which provided less diverse experience with tasks that depend on WM. These were contrasted with two controls, a Same Task (ST) condition in which participants practiced the reading span, exactly the same as the target task, and a Placebo Control (PC) condition, in which participants made speeded judgments to the same verbal stimuli as in the lexical decision task but with no memory component, and hence, no demand to simultaneously manage processing and memory (i.e., WM). We measured both how quickly the target task in Phase 2 was acquired, as well as pre- to posttest change in practiced and unpracticed WM tasks and episodic memory tasks, as a function of prior experience in Phase 1.

According to the Principle of Direct Transfer, training in the reading span in Phase 2 should be accelerated by conditions in Phase 1 that share the most elements with Phase 2 training. Thus, Principle of Direct Transfer predicts an early advantage for the ST group relative to the other three groups that would be sustained through acquisition, as well as some advantage for the two other WM training groups, the DM and DS conditions, relative to the PC condition. The Principle of Mutualism, on the other hand, predicts accelerated acquisition for the DS, and especially the DM, conditions, relative to the PC condition, on par with the ST condition. This is because even though the DS and DM tasks share fewer elements with the target task, the Mutualism principle predicts that the acquisition of the elements that are shared enhances plasticity of the unpracticed elements of the target task. Critically, Mutualism would predict that any advantage of the DS and DM conditions would not be immediately apparent but only emerge with practice.

The two theories also make contrasting predictions for pre- to posttest change. Principle of Direct Transfer would predict greater change in the practiced WM tasks relative to the unpracticed WM tasks for the ST, DS, and DM groups relative to the PC control. Specifically, the ST group — who exclusively practiced the reading span (RS) task in both phases of training would be expected to show the greatest

pre- to posttest improvement in RS, but the least improvement in all other span tasks. The DS group (who practiced the lexical decision span (LDS) in Phase 1 and RS in Phase 2) and the DM group (who practiced the category span (CatS) and LDS) in Phase 1 and RS in Phase 2), however, would be expected to show some improvement in the trained tasks according to their collective exposure across the two phases (i.e., DS=DM on RS; DS>DM on LDS; DM>DS on CatS), and less improvement in the untrained tasks, and even less in the episodic memory task (which would represent far transfer). According to the principle of Mutualism, performance is most likely to be enhanced when elements of the task are acquired and then the target task containing those elements is practiced. This situation is embodied in the DM condition in which the individual acquires multiple elements of the WM task that are then practiced in the context of a new task. Thus, the Principle of Mutualism predicts the largest gains from pre- to posttest for the DM group, and to a lesser extent for the DS group, who had less diverse exposure to elements of the WM task relative to the DM group. Because there was no opportunity to practice the untrained WM tasks or episodic memory task, the Principle of Mutualism does not predict improvement in these areas.

Collectively then, Principles of Direct Transfer and of Mutualism make quite different predictions for performance in the successive enrichment paradigm and in pre- to posttest change. Most importantly, the former predicts the reading span in Phase 2 will be acquired the most quickly and show the largest pre- to posttest gains by the ST group, while the latter predicts faster acquisition and largest pre- to posttest gains by the DM and (to a lesser extent) the DS group.

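### The protocol states Mutualism's Phase 2 prediction for DM and DS against ST in two ways that do not give the same ordering, and the SAP specifies no DM-ST or DS-ST contrast to settle it

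*Combined protocol and SAP*

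**What the plan says.** The Objectives give the Phase 2 predictions twice.

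- **First statement, Direct Transfer:** it "predicts an early advantage for the ST group relative to the other three groups that would be sustained through acquisition", together with "some advantage for the two other WM training groups, the DM and DS conditions, relative to the PC condition".
- **First statement, Mutualism:** it "predicts accelerated acquisition for the DS, and especially the DM, conditions, relative to the PC condition, on par with the ST condition". A further sentence, marked as critical, adds that "any advantage of the DS and DM conditions would not be immediately apparent but only emerge with practice".
- **Closing summary:** presented as the most important contrast. For Direct Transfer, "the former predicts the reading span in Phase 2 will be acquired the most quickly" by ST, whereas "the latter predicts faster acquisition and largest pre- to posttest gains by the DM and (to a lesser extent) the DS group".

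The Design section defines the critical test as whether the four groups differ, with no direction. The Statistical Analysis Plan makes daily mean reading span over the 10 days of Phase 2 a primary outcome. It models this outcome with training day and Phase 1 group as fixed factors and PC as the reference group. The Bonferroni post hoc comparisons among groups belong to the pre- to posttest ANOVA, not to this model.

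**The concern.** The study exists to separate two theories, and for Phase 2 acquisition they part mainly on where ST stands relative to DM and DS. The first statement puts Mutualism's DM and DS level with ST. The summary names ST as the fastest group under one theory and says DM and DS are faster under the other. ST is the only other group in that sentence, so a reader will take it to mean DM faster than ST.

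If both statements stand, a result in which DM equals ST, with both above PC, fits the first but not the summary as naturally read. A result in which DM exceeds ST fits the summary but departs from parity. Either could be written up as what Mutualism predicted. The planned model does not force the issue, because the comparison with ST is not among those it specifies.

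**Working it through.** The question is one of wording, so the statements are set side by side.

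**Step 1. Orderings stated**

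| Source in the Objectives | DM, DS against PC | DM, DS against ST |
|---|---|---|
| Direct Transfer, first statement | some advantage | behind ST throughout |
| Direct Transfer, summary | not stated | ST fastest |
| Mutualism, first statement | faster, DM especially | level with ST |
| Mutualism, summary | comparator not named | comparator not named; natural reading is ahead of ST |

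**Step 2. Readings of the Mutualism summary**

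- *Faster than ST.* This is the natural contrast, but it does not match the parity in the first statement if parity refers to rate.
- *Faster than PC.* This matches the first statement. But Direct Transfer also expects DM and DS to be ahead of PC, so this clause alone would not separate the theories. ST's position and the timing of the advantage would have to do that.
- *Steeper slope, same final level.* DM starts below ST, rises faster and ends level. As an illustration, assume a linear day effect with days coded 0 to 9. The final gap equals the starting gap plus 9 times the slope gap. If DM starts δ below ST and ends level, then −δ + 9 × (slope gap) = 0, so DM's slope exceeds ST's by δ/9 per day. DM is then slower at the start, faster in rate and equal at the end, and both statements can be true. The protocol does not draw this distinction.

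**Step 3. Does the SAP settle it?** With PC as reference, the specified comparisons are DM-PC, DS-PC and ST-PC. DM-ST is (DM-PC) − (ST-PC), and DS-ST is formed likewise. Both can be estimated from the same fitted model, but neither is specified. No equivalence margin is given for parity.

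**Step 4. Precision, as illustration only.** The stated power of .9 cannot be reproduced, because no sample size is given. Two readings of the .43 effect size give the range.

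- As Cohen's f in a four-group ANOVA at alpha .05, power .9 needs N = 81. Balanced, 84 (21 per group) gives .913 and 80 gives .897.
- As Cohen's d, two-sided, it needs 114 per group.

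For a single endpoint with SD 1, the 95% half-width for DM-ST is 1.96 × √(2/n):

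- n = 21: 1.96 × 0.309 = 0.60 SD
- n = 114: 1.96 × 0.132 = 0.26 SD

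Approximate power to show equivalence when the true difference is zero (two one-sided tests, 5% each) is 2Φ(m/SE − 1.645) − 1 for margin m, set to 0 where negative. At m = 0.5 SD:

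- n = 21: m/SE = 1.62, below 1.645, so power is 0
- n = 114: m/SE = 3.78, so power is about 0.97

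Under the smaller size, a non-significant DM-ST difference would say little about parity. These figures describe one cross-sectional endpoint, not the planned 10-day mixed model, and the point about wording does not depend on them.

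**The case against.** The strongest reply is that nothing here is contradictory. The summary uses a comparative for acquisition and a superlative for gains, and a summary is fairly read with the comparators already given, which makes PC the reference. On that reading the theories still differ: Direct Transfer has ST leading throughout, while Mutualism has parity with ST and a delayed advantage. The sentence on emergence with practice also lends some support to the slope-and-level reading, and the outcome is described elsewhere as a rate of learning. Finally, these are narrative predictions, and the Design section asks only whether the groups differ.

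Most of this stands. It shows that the statements can be reconciled, and it rules out calling them a flat contradiction. It does not remove the ambiguity, because the reader has to supply either the comparator or the slope/level distinction. The first statement also attaches parity to accelerated acquisition itself, which makes a purely level-based reading less than obvious.

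A reader might go further and infer that the protocol sets two incompatible success rules, so that Mutualism would be declared supported almost whatever the DM-ST difference. The documents do not support that. They contain no decision rule for choosing between the theories, and DM failing to exceed PC, or falling clearly below ST, would count against Mutualism on either statement. Any probability of claiming support would depend on an assumed sample size, an assumed DM-PC effect and rules that the documents do not state.

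**Conclusion.** The point holds as an unresolved ambiguity about DM and DS against ST on a primary outcome, together with a Phase 2 analysis that does not specify the comparison that would resolve it. Parity and DM ahead of ST could each be presented as the pre-stated Mutualism result. The data and the fitted model are unaffected; what is at risk is how the theory test is interpreted. The conclusion rests on the text alone: the summary names no comparator, and neither statement separates starting level, slope and final level. It is worth correcting, but it does not invalidate the trial.

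**What to change.** 1. **Objectives.** Name the comparator in the closing summary and reconcile it with the first statement. Give one DM-ST and one DS-ST ordering, separately for starting level, slope across days and final level.
2. **SAP.** Add the DM-ST and DS-ST contrasts (group and group-by-day) to the Phase 2 mixed model, with confidence intervals. State how day is coded, so that it is clear which day the group contrast refers to. Say that a non-significant difference will not be read as parity.
3. **Reporting.** The Methods section gives an observed pretest-posttest interval (mean 34.5 days, SD 7.0) with a between-group test, so the trial has been run. The parity prediction should not now be replaced by a directional one. Any clarification should be dated and labelled as made after the fact. The report should give the estimates and state that the protocol's wording supported both predictions.

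The cost is a few sentences and contrasts from a model already planned; no new data are needed. The downside is that one outcome can no longer be presented as the single pre-stated confirmation of Mutualism, and the DM-ST intervals may be wide.

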### ***Statistical Analysis Plan***

The primary outcomes were (a) standard unit change in cognitive measures from pre- to posttest (i.e., posttest score - pretest score) / standard deviation at pretest) for reading span and a composite of work and (b) daily mean reading span score achieved across the 10 days of training in Phase 2. For the latter variable, calculations were based on scores from Trial 2 to the end of the training block (we discarded Trial 1 because this trial only included one element to remember and thus, elicited uniform performance across participants). Pre- to posttest change was analyzed using one-way ANOVA to test differences among the four groups with post hoc Bonferroni comparisons to correct for the number of

comparisons. Acquisition of the reading span in Phase 2 (change across the 10 days of practice) was analyzed with mixed-effects linear regression using the lme4 and lmerTest packages for R version 4.2.2 (R Core Team, 2022). The PC Group was set as reference in comparisons with other groups in an analysis with Training Day and Phase 1 Training Group as the fixed factors, and by-subject random intercept, using the restricted maximum likelihood (REML) method of estimation. The design was powered at .9 to detect an effect size of .43 for differences between the groups with an alpha of .05, and to detect an effect size of .14 for group differences in change across 10 days (Faul et al., 2007), though of course, there estimates of power for linear mixed-effects models are controversial. There was no correction for the number of tests in this latter analysis.

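### Some predictions that separate the two theories are predictions of no difference, but the SAP plans only tests of difference and does not estimate DM−ST or DS−ST in Phase 2 acquisition

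*Combined protocol and SAP*

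**What the plan says.** **Predictions (Study Protocol, Objectives).**
- For Phase 2 acquisition, Direct Transfer expects an early ST lead that lasts. Mutualism expects faster learning in the DS and especially the DM "conditions, relative to the PC condition, on par with the ST condition". This prediction has two parts: better than PC, and level with ST.
- Mutualism also holds that "any advantage of the DS and DM conditions would not be immediately apparent but only emerge with practice".
- For pre- to posttest change, Direct Transfer predicts "DS=DM on RS; DS>DM on LDS; DM>DS on CatS". The first item is an equality. Mutualism instead puts DM ahead of DS.
- The closing summary, which the protocol presents as the most important contrast, is directional. Direct Transfer has ST learning fastest and gaining most, while "the latter predicts faster acquisition and largest pre- to posttest gains by the DM and (to a lesser extent) the DS group".

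**Analysis (Statistical Analysis Plan).** Pre- to posttest change is analysed by "one-way ANOVA to test differences among the four groups with post hoc Bonferroni comparisons". Phase 2 acquisition is analysed by a linear mixed model with Training Day and Phase 1 group as fixed factors, a by-subject random intercept and PC as the reference group. Power is given only for detecting differences. The SAP names no equivalence test, margin, confidence-interval rule or other rule for reading a non-significant result.

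**The concern.** A test of difference can refute an equality prediction but cannot confirm it. If ST and DM do not differ significantly, they may be alike or the study may be too imprecise to tell, and the plan gives no way to say which. The gap is widest for acquisition. With PC as reference, the fitted coefficients are DM−PC, DS−PC and ST−PC, so parity with ST would have to be judged by eye from two separate comparisons with PC. The same issue applies to equal reading span gains in DS and DM, where a small real DM advantage, which Mutualism predicts, could easily go undetected.

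At stake is the inference that the study was built to make, namely which of two theories the data favour.

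**Working it through.** **1. Sample size implied by the plan.** The SAP gives power .9, effect size .43 and alpha .05, but neither N nor the effect metric. Reading .43 as Cohen's f in a four-group one-way ANOVA, the noncentrality is f²N = .1849 × N. Power is .897 at N = 80, .901 at N = 81 and .913 at N = 84, so the stated power is reproduced at about 20 per group. The second planning figure, .14 for group differences in change over 10 days, gives N = 77 if read as f with an assumed correlation of .5 between days (152 at correlation 0, 33 at .8). This makes the f reading plausible but does not prove it. If .43 is Cohen's d for two groups, n = 2 × ((1.96 + 1.28)/.43)² ≈ 114, or about 115 per group.

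**2. Precision for one pair on a single score, 20 per group (SD = 1, pooled error, 76 df).** The standard error is √(2/20) = .316. The 95% half-width is 1.99 × .316 = .63 SD.

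**3. Parity with ST when it is false.** Assume DM lies exactly midway between PC and ST. The Mutualism pattern needs DM > PC significant and DM−ST not significant, each at two-sided .05 without correction. The two comparisons share the DM mean, so the joint rate was simulated. The largest lead shown is the one that gives f = .43 with PC and ST at the extremes and the other two groups midway: f = L/√8, so L = .43 × 2.83 = 1.22.

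| True ST−PC lead (SD) | DM−ST not significant | DM > PC significant and DM−ST not significant |
|---|---|---|
| .5 | 88% | 12% |
| .8 | 76% | 22% |
| 1.0 | 66% | 29% |
| 1.22 | 52% | 33% |

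The last column is the relevant one, because the prediction has two parts.

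**4. DM−DS on reading span gain, Bonferroni over six pairs (alpha .05/6).** The critical t is about 2.71. For a gap of .5 SD the noncentrality is .5/.316 = 1.58 and power is .137, so the gap is missed in 86% of trials. For a gap of .25 SD it is missed in 97%.

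**5. If .43 is d (about 115 per group).** The DM−DS gap is missed in 77% (.25 SD) and 13% (.5 SD). For parity with ST, a lead of .5 SD at 115 per group is equivalent to .5 × √(115/20) = 1.20 SD at 20 per group, so the misleading pattern still occurs in about 33%. For a lead of .8 SD the DM−ST gap is .4 SD, with noncentrality .4 × √(115/2) = 3.03. It is missed in about 14%, so the pattern occurs in at most 14%, and less for larger leads.

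**6. Precision in the mixed model.** Assume a daily residual SD of .5 and the planned random-intercept model. For linear change from Day 1 to Day 10, the standard error of a group difference is 9 × (.5/√82.5) × √(2/20) = .157, where 82.5 is the sum of squared deviations of days 1 to 10. The 95% half-width is 1.96 × .157 = .31 SD, about half the single-score figure. Without a random slope, however, this standard error could be too small.

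**The case against.** Several points on the other side are sound.

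- **The parity prediction is not met by a null result alone.** DM must also beat PC. A reader might take the 52% to 88% in the middle column as the rate of false support for Mutualism. The protocol's wording does not allow that, and the joint rate is 12% to 33%.
- **The delayed-advantage prediction is about a growing difference.** The SAP analyses change across the 10 days with group and day as factors, and it quotes power for group differences in that change. It plans no separate Day 1 test, so a reader should not infer that a non-significant Day 1 will be counted for Mutualism. What remains is that the Day-by-Group interaction is implied, not written out.
- **The single-score figures do not carry over directly to acquisition.** Step 6 shows that precision for 10-day change may be clearly better. They apply most directly to the pre- to posttest analysis.
- **The main contrast is directional.** A reader might infer that the same data could support both theories. But parity with ST concerns acquisition and DS = DM concerns reading span gain, and on the main contrast ST and DM cannot both lead on one outcome.
- **Nothing in the documents says that non-significance will count as support.** That can only be inferred from the absence of any other rule.
- **The statement that DM learns faster names no comparator.** It may mean faster than PC, which would agree with parity with ST. It stands opposite the claim that ST learns fastest, so the other reading is open too.

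None of this supplies the missing DM−ST and DS−ST estimates or a rule for interpreting them.

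**Conclusion.** The point holds in limited form. Some of the predictions that separate the theories, not all of them, are predictions of no difference, and the plan has no analysis that can support these. In acquisition, the DM−ST and DS−ST contrasts are not estimated at all.

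At about 20 per group, with DM truly midway, the pattern that Mutualism predicts on a single score arises in about 12% to 33% of trials, and a true DM−DS gap of .25 to .5 SD is missed after Bonferroni in about 97% to 86%. These figures rest on an N that the documents do not state, on reading .43 as Cohen's f, and on a single-score analysis. Under the d reading the problem is smaller for DM−DS and for larger ST−PC leads, but not for a lead of .5 SD.

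The documents do not support the conclusion that the plan will treat imprecision as evidence, only that it does not rule this out. The ANOVA and the mixed model can stay.

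**What to change.** 1. From the same mixed model, estimate DM−ST and DS−ST, both in level and in Day-by-Group change, with 95% confidence intervals. Report the DM−DS difference in reading span gain with its interval.
2. Write the Day-by-Group interaction into the model statement. Judge the prediction that an advantage "would not be immediately apparent but only emerge with practice" by the change in DM−PC and DS−PC over days, and show the Day 1 estimate with its interval.
3. State that a non-significant difference alone supports neither theory, and that equality is inconclusive when the interval includes meaningful differences.
4. Reconcile the two statements on DM versus ST in the Objectives (level with ST, or faster), and name the comparator.

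The contrast DM − (ST + PC)/2, which asks whether DM keeps more than half of the ST−PC lead, may be added as a supplementary analysis. The half-lead threshold is a choice, so label it post hoc if it is set after the data were seen. State its power as well: if DM truly equals ST and ST > PC must also be significant, power is about 5% to 57% for leads of .5 to 1.22 SD at 20 per group.

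The cost is some SAP wording and a few contrasts, with no new data. The downside is that some comparisons will have to be reported as inconclusive. For DS = DM this is likely, since at 20 per group the 95% interval for a single-score pair extends .63 SD either side.
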